10.2 Statistical plan

Disease-free survival and overall survival in treated patients will be analyzed with a Cox proportional hazards regression, first univariable and then multivariable.

Change between T0 (28 days after RT) and T1 (24 months) in secondary endpoints, all recorded as continuous variables, will be modelled using linear mixed models (or GEE), accounting for within patient repetition. The interaction between time and ALC status will be the effect of interest. All models will adjust for potentially confounding clinical variables.

.11.SCHEDULE OF EVALUATION

Evaluation	Screening	TREATMENT PERIOD			Follow up at 24 months
		Day -1	RT treatment (period 0)	Day +28 (from the end of RT)	
Informed consent	X				
Inclusion/exclusion criteria	X				
Medical history	X				
ECOG PS Status	X				
Vital signs	X				
Evaluation of high-risk factors for recurrence	X				
RT treatment			X		
RT characteristics (site-volume-dose)			X	X	
Immune markers *		X		X	
Molecular profile		X			
Outcomes: DFS and OS					X

*circulating T cells CD3+CD8+ and CD3+CD4+

absolute lymphocyte (ALC) count and neutrophil counts (ANC) and neutrophil/lymphocyte ratio (NLR)

Treg lymphocytes, defined as CD4+CD25+FOXP3+ or CD4+CD25hi+CD39+ cells.

Naïve/Memory T lymphocytes CD4+ and CD8+ (defined as CD45RA/CD45RO)

myeloid-derived suppressor cells, defined as cells expressing Lin-neg (CD3, CD14, CD15, CD19, CD56) /HLA-DR-/CD33+/CD11b+ in either a “lymphocyte” (small FSCxSSC) gate, or in a “monocyte” (larger FSCxSSC) gate, and as HLA-DR+/lo CD14+ cells in a large gate.

Plasmacytoid Dendritic Cells (CD303+CD123+)

NK cells dim (CD3-CD16+CD56+) and bright (CD3-CD16-CD56++);

NKT cells (CD3+CD56+);

Myeloid Dendritic cells (CD1c+ and CD141+);

Monocytes subsets (classical CD14+CD16-, intermediate CD14+CD16+, non classical CD14+/-CD16+);

B lymphocytes (CD19);

Analyses of plasma cytokines (TNFalpha, TGFbeta, IL-6, IL-10) by ELISA;

IFN signature: real-time PCR on mRNA from PBMCs

Any other treatment performed by the patient in case of progression will be collected and reported in the CRF.

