2.2.1. Secondary objectives

Secondary objectives include:

- Evaluation of changes (Δ) in the circulating immune-cells population at two time points (before and after RT);
- Correlation between DFS and circulating immune cell population before and after RT;
- Evaluation of changes in immune cell population according to the primary site (h&n vs non-h&n), volume (cc) and administered dose (50 Gy; 50-60 Gy; >60 Gy depending on margins involvement) of irradiation. The same parameters will be evaluated according to the nodal basin irradiation in terms of levels included in CTV-HR vs CTV-LR (levels, volume and dose).
- Evaluation of changes (Δ) in the circulating immune-cells population in the subgroup of patients defined as "immunosuppressed" (i.e. patients with chronic hematologic malignant neoplasm, or HIV, or AIDS, or who were treated with immunosuppressive therapies for organ transplantation 6 months or more prior to diagnosis) in respect of non-immunosuppressed patients;
- Evaluation of changes (Δ) in the circulating immune-cells population according to RT induced toxicities;
- 2-year Overall Survival (OS)

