2.2.2. Secondary outcome

Secondary outcomes include:

- Changes in white cells blood sub-population defined by the difference between two time points: the day before adjuvant RT (day -1) to day 28 (+/- 3 days) after RT.

In particular, we will evaluate changes of:

- circulating T cells CD3+CD8+ and CD3+CD4+

- absolute lymphocyte count (ALC) and neutrophil counts (ANC) and neutrophil/lymphocyte ratio (NLR)
- Treg lymphocytes, defined as CD4+CD25+FOXP3+ or CD4+CD25hi+CD39+ cells.
- Naïve/Memory T lymphocytes CD4+ and CD8+ (defined as CD45RA/CD45RO)
- myeloid-derived suppressor cells, defined as cells expressing Lin-neg (CD3, CD14, CD15, CD19, CD56) /HLA-DR-/CD33+/CD11b+ in either a “lymphocyte” (small FSCxSSC) gate, or in a “monocyte” (larger FSCxSSC) gate, and as HLA-DR+/lo CD14+ cells in a large gate.
- Plasmacytoid Dendritic Cells (CD303+CD123+)
- NK cells dim (CD3-CD16+CD56+) and bright (CD3-CD16-CD56++);
- NKT cells (CD3+CD56+);
- Myeloid Dendritic cells (CD1c+ and CD141+);
- Monocytes subsets (classical CD14+CD16-, intermediate CD14+CD16+, non classical CD14+/-CD16+);
- B lymphocytes (CD19)
- Analysis of plasma cytokines (TNFalpha, TGFbeta, IL-6, IL-10) by ELISA;
- IFN signature: real-time PCR on mRNA from peripheral blood mononuclear cells (PBMCs)

- DFS of patients according to the values of the above reported immune population at baseline, after RT and according to the changes before/after RT

- Changes in immune population cell at the two time points according to the following variables:

- Site of irradiation (involving or not nodal basins, head and neck vs non-head and neck area and lymphnodes levels involved in CTV-HR vs CTV-LR)
- Volume of irradiation (expressed as cc) for primary site and nodal basin (volume received by lymphnodes classified as CTV-HR vs CTV-LR)
- Dose of irradiation (total dose received in Gy) for primary site (depending on the margin status) and nodal basin (dose received by lymphnodes classified as CTV-HR vs CTV-LR)

- Changes in immune population cells in the immunosuppressed patient subgroup in comparison with non-immunosuppressed patients

- Changes in immune population cells according to RT related toxicities as mucositis and radiodermatitis

- 2-year OS

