4. STUDY DESIGN

4.1. Overview

The patients enrolled in the study are affected form cSCC classified at high risk and addressed to surgery and subsequent adjuvant RT according to clinical practice. The aim of the study is to evaluate patients' outcome according to the post-radiation lymphocytes count and to the changes induced in the immune cell population by a loco-regional treatment as radiotherapy.

The way to objectivate these results is to collect some blood samples and analyze them.

The study comprises blood samples collection performed at two time points:

- at baseline (day -1) before adjuvant RT;
- at day 28 (+/- 3) after RT completion.

At any timepoints blood samples will be analyzed for immune cell population detailed in 2.1.2 and 2.2.2 paragraphs.

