4.2 Follow up

After the completion of the study analysis at day 28 (+/- 3 days) after radiotherapy, the patients will remain in follow up.

The follow up of will be carried out according to clinical practice, with periodic visits and instrumental assessments, which should performed with the following timepoints:

- Clinical examination every 3 months for the first year, then every 6 months
- Radiological imaging 3 months after RT completion, then every 6 months

Disease free survival of the patients, overall survival, possible side effects and other treatments performed in adjuvant or palliative settings will be collected.

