6. ASSESSMENT OF EFFICACY

Blood samples will be collected at two time point to assess immune-modulating effects of adjuvant radiotherapy.

The following blood cells will be assessed at baseline (day -1) before adjuvant RT and at day 28 (+/- 3) after RT completion:

- circulating T cells CD3+CD8+ and CD3+CD4+
- absolute lymphocyte (ALC) count and neutrophil counts (ANC) and neutrophil/lymphocyte ratio (NLR)
- Treg lymphocytes, defined as CD4+CD25+FOXP3+ or CD4+CD25hi+CD39+ cells.
- Naïve/Memory T lymphocytes CD4+ and CD8+ (defined as CD45RA/CD45RO)
- myeloid-derived suppressor cells, defined as cells expressing Lin-neg (CD3, CD14, CD15, CD19, CD56) /HLA-DR-/CD33+/CD11b+ in either a “lymphocyte” (small FSCxSSC) gate, or in a “monocyte” (larger FSCxSSC) gate, and as HLA-DR+/lo CD14+ cells in a large gate.
- Plasmacytoid Dendritic Cells (CD303+CD123+)
- NK cells dim (CD3-CD16+CD56+) and bright (CD3-CD16-CD56++);
- NKT cells (CD3+CD56+);
- Myeloid Dendritic cells (CD1c+ and CD141+);
- Monocyte subsets (classical CD14+CD16-, intermediate CD14+CD16+, non classical CD14+/-CD16+);
- B lymphocytes (CD19+);
- Analysis of plasma cytokines (TNFalpha, TGFbeta, IL-6, IL-10) by ELISA;
- IFN signature: real-time PCR on mRNA from PBMCs

A centralized evaluation of all blood and tissue samples collected will be performed at the Department of Molecular and Translational Medicine, Oncological-Immunological Experimental Section, University of Brescia.

Follow up of all subjects enrolled will be conducted according to clinical practice, with periodic visits and instrumental assessments. Survival status of the patients and possible other treatments performed will be collected for at least 24 months.

Plasma and mRNAs will be stored at the Department of Molecular and Translational Medicine, Oncological-Immunological Experimental Section, University of Brescia. All samples will be identified by a specific numerical code.

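### Section 10.2 models immune-marker change from day 28 to 24 months, but the markers are sampled only at day -1 and day 28

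*Combined protocol and SAP*

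**What the plan says.** Section 10.2 assigns DFS and OS to Cox regression. It then gives one model for change, a linear mixed model or GEE with repeated measures within patient, applied to "Change between T0 (28 days after RT) and T1 (24 months) in secondary endpoints, all recorded as continuous variables". It names the interaction of time with ALC status as the effect to be estimated, with adjustment for clinical confounders.

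The rest of the document uses a different pair of times:

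- Section 2.2.1, first objective: change in the circulating immune-cell "population at two time points (before and after RT").
- Section 2.2.2: the outcome is "defined by the difference between two time points: the day before adjuvant RT (day -1) to day 28 (+/- 3 days) after RT".
- Section 4.1: "The study comprises blood samples collection performed at two time points", listed as day -1 and day 28 (+/-3).
- Section 6: "The following blood cells will be assessed at baseline (day -1) before adjuvant RT and at day 28 (+/- 3) after RT completion".
- Section 11, schedule of evaluation: the immune-markers row is marked at Day -1 and Day +28. The 24-month column carries a single mark, for "Outcomes: DFS and OS".

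On the later period, section 4.2 says "After the completion of the study analysis at day 28 (+/- 3 days) after radiotherapy, the patients will remain in follow up". It lists clinical examination and imaging, with collection of DFS, OS, side effects and other treatments. Section 6 adds: "Survival status of the patients and possible other treatments performed will be collected for at least 24 months".

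**The concern.** The time points in the analysis model overlap the sampling plan at day 28 only. The model needs a second marker value at 24 months, which nobody is asked to collect, and it ignores the day -1 value, which everybody is asked to give.

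Objectives 1, 3, 4 and 5 of section 2.2.1 concern the change from before to after radiotherapy: overall, by site, volume and dose, by immunosuppression, and by toxicity. Section 10.2 contains the only model for change, and that model does not address this contrast. If the text is followed, these four objectives cannot be analysed. If it is quietly set aside, the analysis of a long list of markers is chosen once data are in hand. Section 4.3 puts the before/after change among the results to be looked at in the 24-month interim analysis, so the text needs to be right before then.

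**Working it through.** The plan gives no power or precision figure for the marker analysis. The check is therefore a comparison of time points followed by a count.

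**1. Time points side by side**

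| Place | Marker times |
|---|---|
| 2.2.1 | before RT, after RT |
| 2.2.2 | day -1, day 28 (+/-3) |
| 4.1 | day -1, day 28 (+/-3) |
| 6 | day -1, day 28 (+/-3) |
| 11, schedule | Day -1, Day +28 |
| 10.2, model | day 28, 24 months |

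**2. Values and pairs.** Inputs: 42 patients (sections 4.4 and 10.1); planned samples per patient are 1 at day -1, 1 at day 28 and 0 at 24 months. All counts are maxima, before missing samples.

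- Planned marker values: 42 x 2 = 84.
- Values the 10.2 model can use: 42 x 1 at T0 plus 42 x 0 at T1 = 42.
- Within-patient pairs under 10.2: 42 x 1 x 0 = 0.
- Within-patient pairs for the 2.2.2 outcome: 42 x 1 x 1 = 42.

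**3. What can be estimated.** Section 10.2 does not write the model out. The smallest form containing the stated interaction is

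mean = b0 + b1 (time) + b2 (ALC status) + b3 (time x ALC status).

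If every observation is at T0, time is constant. Coded 0, the columns for b1 and b3 are all zero, so the design matrix has rank 2 of 4. The two terms lost are the change and the interaction. Adding clinical covariates does not restore them. With day -1 and day 28 observed in the planned groups of 17 and 25 (section 10.1), all four time-by-group cells are filled and the rank is 4 of 4.

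**4. Precision once the times are corrected.** The unadjusted 95% CI half-width for a mean change, in units of the SD of the change, is t(0.975, n-1)/sqrt(n).

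- n = 42 complete pairs: 2.020/6.481 = 0.312.
- n = 34 complete pairs (an assumption, to show the effect of missing samples): 2.035/5.831 = 0.349.

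**5. Other readings of the 10.2 sentence**

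- *It refers to other secondary endpoints.* The remaining ones are DFS by marker level and 2-year OS. Both are time-to-event, and the same section gives DFS and OS to Cox regression.
- *The 24 months comes from the interim analysis.* Section 4.3 gives 24 months as a date of analysis, not of sampling, and names the before/after change as what will be analysed. This may explain the slip, and it confirms the intended contrast.
- *Day -1 enters as a covariate.* Only clinical variables are named for adjustment.
- *Routine follow-up counts supply T1.* No section lists them as study data, and they could not be presumed to provide the flow-cytometry subsets, ELISA cytokines or IFN signature.

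**The case against.** The strongest reply is that this is a labelling error in one sentence about secondary endpoints. The intended contrast is stated consistently elsewhere, the right samples are scheduled, no data are lost, and the text can be corrected at any time before analysis. The day -1 values are also not unused in the plan as a whole, since section 2.2.2 relates DFS to baseline marker levels as well. All of this is fair. It shows that the correction is easy and that the primary analysis is safe. It does not make the sentence executable, and that sentence is the only model the plan gives for marker change.

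Two further points deserve weight. The rank count in step 3 rests on a minimal model that the plan does not spell out; the absence of any pair does not depend on it. The half-widths in step 4 describe what the corrected analysis would deliver and are not evidence of the error.

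**Conclusion.** The plan is wrong as written on this point and needs correcting before any marker analysis. The stated model has 0 of 42 within-patient pairs, cannot estimate the change or the interaction it names, and omits the day -1 sample. Four of the six secondary objectives are affected; the primary DFS comparison, the Cox models and the sample size are not. The model class is usable, and only its time points are at fault. The conclusion rests on the sampling times in the document and on no outside figure. It would change only in part if a 24-month sample had been intended, because day -1 would still be missing from the model for the before/after objectives.

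A caution applies once the times are corrected. ALC status is defined by ALC after radiotherapy, and day 28 is the only planned sample after it. For ALC, NLR and any lymphocyte subset expressed as an absolute count, the grouping variable is then the outcome or part of it. The size of that artefact depends on SDs and correlations the documents do not give, so it is not quantified here.

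**What to change.** 1. The sponsor confirms that no 24-month blood sample was intended.
2. In section 10.2, set T0 = day -1 before radiotherapy and T1 = day 28 (+/-3) after its completion, and remove 24 months from the marker model.
3. Report the time effect with its 95% CI as the before/after change. Use time-by-factor terms for the objectives on site, volume and dose, immunosuppression, and toxicity.
4. Keep the time-by-ALC-status interaction if wanted, but label it descriptive for ALC, NLR and any lymphocyte subset reported as an absolute count.

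The cost is a few sentences in 10.2, with no new samples, visits or patients. If a 24-month sample was in fact intended, up to 42 further samples would be needed, together with changes to sections 2.2.1, 2.2.2, 4.1, 6 and the schedule, and day -1 would still have to be added to the model.

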2.1.2. Primary outcome

Primary outcome consists of disease-free survival (DFS) of patients with ALC < 500 cells/mL after radiotherapy treatment.

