10. STATISTICAL ANALYSIS

<https://www.sample-size.net/> (Kohn MA, Senyak J. Sample Size Calculators [website]. UCSF CTSI. 29 April 2021) has been used to calculate the sample size. We consider the expected rate of patients with ALC less than 500 cells/mL being 40% one month after RT end, according to previous works showing this rate being 30% at 3 months in head and neck cancer series treated with RT (18), and the estimated 3-year recurrence-free survival being 36% in patients with ALC less than 500 cells/mL and 63% in patients with ALC greater than 500 cells/mL, so HR=0.45 (JAMA Otolaryngol Head Neck Surg. 2019;145(5):413-421. doi:10.1001/jamaoto.2019.0034).

All statistical analyses will be performed using SPSS version 23.0 (SPSS, Chicago, IL).

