10.1 Sample size calculations

To test the Hazard Ratio between Group0 (patients with ALC less than 500 cells/mL) and Group1 (patients with ALC greater than 500 cells/mL) of 0.3 with type I error rate of 5% and power of 80%, we need a minimum of 23 total events which in our hypothesis of median survival time in Group 0 equal to 18 months, 5% censoring rate and whole duration of the study of 4 years correspond to 42 patients, 17 in the Group0 and 25 in the Group1..

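### Section 10.2 targets a time-by-ALC-status interaction that no secondary objective asks for and that is biased for ALC, NLR and absolute lymphocyte-subset counts

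*Combined protocol and SAP*

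**What the plan says.** Section 10.2 models "Change between T0 (28 days after RT) and T1 (24 months) in secondary endpoints, all recorded as continuous variables" with linear mixed models or GEE, adjusted for clinical confounders. It then singles out one term: "The interaction between time and ALC status will be the effect of interest".

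Section 10.2 does not define ALC status. Elsewhere it is the post-RT count cut at 500: the primary outcome (2.1.2) is DFS in "patients with ALC < 500 cells/mL after radiotherapy treatment", and section 10.1 compares "Group0 (patients with ALC less than 500 cells/mL) and Group1 (patients with ALC greater than 500 cells/mL) of 0.3". Section 10 places the cut at about one month, with the "expected rate of patients with ALC less than 500 cells/mL being 40% one month after RT end". That is the day 28 sample.

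The first secondary objective in 2.2.1 is "Evaluation of changes (Δ) in the circulating immune-cells population at two time points (before and after RT"). The others relate DFS to the immune populations, or ask how marker change varies with primary site, irradiated volume, dose, nodal irradiation, immunosuppression and toxicity. The last is 2-year OS. The outcome list in 2.2.2 includes ALC, NLR, CD4 and CD8 T cells, Treg, naive/memory, NK, NKT and B cells alongside myeloid, dendritic and monocyte populations, cytokines and an IFN signature. No section exempts the ALC-derived markers from the interaction model.

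**The concern.** There are two problems. First, the term named as the effect of interest answers none of the listed secondary questions, while the terms that would answer the questions about differences in change are not named. Covariate adjustment does not fill that gap: a main effect for site or dose does not test whether change differs by site or dose.

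Second, patients are grouped on a measurement that is also one of the two outcome values. A patient can fall below 500 at day 28 partly through measurement error or ordinary fluctuation, and that same deviation enters the change score. The groups then tend to differ in change even when RT has the same average effect in both. At stake is a report that low-ALC patients lose more lymphocytes of various kinds, read as biology, when some or all of it comes from how the groups were formed.

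**Working it through.** **Plan's own figures.** The documents give no figure for this interaction. The only design calculation concerns DFS, and its event count reproduces: (1.960 + 0.842)² / [0.4 × 0.6 × (ln 0.3)²] = 7.849 / 0.3479 = 22.6, rounded up to 23. No marker quantity enters it, so the sample size is untouched by this point.

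**Named effect against listed questions.**

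| Question in 2.2.1 / 2.2.2 | Term needed | Named in 10.2? |
|---|---|---|
| Change from before to after RT | time | not as the effect of interest, though the model contains it |
| Change by site, volume, dose, nodal irradiation | time × factor | no |
| Change by immunosuppression | time × subgroup | no |
| Change by toxicity | time × toxicity | no |
| DFS by marker level or change; 2-year OS | Cox model | DFS and OS by Cox regression |
| Change by ALC status | time × ALC status | yes, but not a listed question |

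**Direction and size of the bias.** Let X and Y be log ALC at day -1 and day 28, with common SD σ and correlation r, and let the mean RT shift δ be the same for everyone. Then E[Y − X | Y] = δ + (1 − r)(Y − mean of Y). With the lowest 40% of Y as the low-ALC group (0.40 × 42 = 16.8, the plan's 17), the group difference in mean change is −(1 − r)σD, where D = φ(z₀.₄)(1/0.4 + 1/0.6) = 0.3863 × 4.1667 = 1.61.

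Assuming σ = 0.5, σD = 0.805:
- r = 0.3: −0.7 × 0.805 = −0.563, a spurious ratio of change of exp(−0.563) = 0.57.
- r = 0.5: −0.402, ratio 0.67.
- r = 0.7: −0.241, ratio 0.79.
- r = 0.9: −0.080, ratio 0.92.

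**Other markers.**
- Absolute subset count: log subset = log ALC + log fraction. If the fraction is independent of ALC, the bias is the same; the fraction only adds noise.
- NLR: log NLR = log ANC − log ALC. The bias has the same size and opposite sign, so the low-ALC group shows a larger apparent rise (ratio exp(0.563) = 1.76 at r = 0.3).
- Subset as a percentage of lymphocytes: log ALC cancels, so there is no mechanical bias.

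**Which pair of visits.** With day -1 and day 28, ALC status is a cut of the second value, and the low-ALC group appears to fall more. With the day 28 and 24-month pair written in 10.2, it is a cut of the first value. The sign reverses, and the low-ALC group appears to recover more (ALC ratio 1.76 at r = 0.3, 1.08 at r = 0.9, if SD and correlation are the same). The schedule has immune samples only at day -1 and day 28.

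**How often the test rejects.** Simulation: 42 patients, lowest 17 by post-RT ALC, same mean RT effect, t-test on the log change (equivalent to time × group with two complete visits). Assumed log SDs: ALC 0.5, ANC 0.4, subset fraction 0.3. The ANC correlation is set equal to r; the subset fraction's own correlation is 0.8. Nominal level 5%.

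| r | 0.3 | 0.5 | 0.7 | 0.8 | 0.9 |
|---|---|---|---|---|---|
| ALC | 91% | 76% | 51% | 36% | 21% |
| Absolute subset count | 87% | 68% | 42% | 28% | 14% |
| NLR | 68% | 51% | 33% | 24% | 14% |

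Subset percentages, and a marker unrelated to ALC, stay at about 5%. If the subset fraction's correlation is set equal to r instead of 0.8, the subset rates run from 79% (r = 0.3) to 16% (r = 0.9), the same pattern.

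**The case against.** The strongest reply is that low-ALC patients may truly lose more cells, so the interaction could be real. That is possible. If the scatter in individual change is biological, the low-ALC patients did fall further. But groups formed on the day 28 value cannot separate that from fluctuation, and for ALC the statement is then close to a tautology.

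Three narrowing points stand. The direction depends on the visit pair, and the pair in 10.2 contradicts the sampling schedule; that must be reconciled first, though the bias is present under either pair. The documents do not say whether subsets are counts or percentages, and percentages escape the mechanical bias. The time effect sits in any model with a time interaction, so the first secondary objective is not left without an analysis.

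A reader might infer more than the documents support:
- That the selection guarantees a larger fall. It biases toward one. The bias shrinks to zero as r approaches 1, and r is unknown.
- That every immune marker is affected. Myeloid cells, dendritic cells, monocytes, cytokines and the IFN signature are not derived from the lymphocyte count.
- That the DFS result is compromised. The Cox comparison by ALC group does not use this interaction.

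It could also be said that ALC status is the study's central grouping, so using it here is natural. Section 4.1, however, presents the post-RT count and the immune changes as two things to relate to outcome. It does not make one a grouping factor for the other.

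**Conclusion.** The point holds in limited form and should be fixed before analysis. As written, 10.2 designates a contrast that no secondary objective requests and names no term for the differences in change that are requested. For ALC, NLR and subsets analysed as absolute counts, that contrast is biased away from zero. The direction follows from the grouping rule and the visit pair whenever the correlation between visits is below 1. The size is illustrative, since the SDs, the correlations and the independence of the subset fraction are assumptions; even at r = 0.9 the rejection rate is about three to four times nominal (14% to 21% against 5%). The consequence is confined to secondary marker analyses.

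**What to change.** In 10.2:
1. State that the effect of interest for each marker is the change from day -1 to day 28 (the time effect), which also aligns the visit labels with the schedule.
2. List time by site, volume, dose, nodal irradiation, immunosuppression and toxicity as exploratory interactions, reported with confidence intervals.
3. Drop the time-by-ALC-status term for ALC, NLR and absolute lymphocyte-subset counts. If it is kept at all, limit it to markers not derived from the lymphocyte count and label it descriptive.
4. State whether each subset is analysed as an absolute count or as a percentage of lymphocytes.

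The cost is SAP wording; no new data are needed. One headline contrast is lost, and the added interactions will be imprecise with 42 patients, which is why they should carry an exploratory label.

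### Section 10.2 makes a time-by-ALC-status interaction the target for the immune markers but fixes no analysis scale, and the result depends on that choice

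*Combined protocol and SAP*

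**What the plan says.** Section 10.2 plans one model for the secondary endpoints, "all recorded as continuous variables, will be modelled using linear mixed models (or GEE), accounting for within patient repetition", and then names its target: "The interaction between time and ALC status will be the effect of interest". Section 2.2.2 describes the main secondary outcome as "Changes in white cells blood sub-population defined by the difference between two time points". The marker list there includes ALC, neutrophils, NLR, many lymphocyte and myeloid subsets, and "Analysis of plasma cytokines (TNFalpha, TGFbeta, IL-6, IL-10) by ELISA".

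Neither section mentions a transformation, a link function, percentage change, a residual check or adjustment for the marker's own baseline. Section 10.2 promises adjustment for clinical confounders but does not name them.

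ALC status comes from the count after radiotherapy. The primary outcome in section 2.1.2 is "disease-free survival (DFS) of patients with ALC < 500 cells/mL after radiotherapy treatment", and section 10.1 uses the same cut for its two groups.

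The time points disagree. Section 10.2 models "Change between T0 (28 days after RT) and T1 (24 months) in secondary endpoints", whereas section 6 says "The following blood cells will be assessed at baseline (day -1) before adjuvant RT and at day 28 (+/- 3) after RT completion". The schedule of evaluation also shows no marker sample at 24 months.

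**The concern.** An interaction can exist on one scale and vanish on another, so a plan that makes an interaction its target has to name the scale. A linear model for continuous values, with change defined as a difference, reads most naturally as a comparison of absolute changes.

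The grouping makes this matter. Patients who finish below the ALC cut will tend to have started lower, and lymphocyte subsets are likely to follow. If radiotherapy removes the same fraction of cells in everyone, the group that starts lower loses fewer cells. The raw-scale test would report that as a different response to radiotherapy. Counts and cytokines are also typically right-skewed, so a raw-scale test can miss a real difference in proportional change.

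**Working it through.** **Inputs from the documents.** Section 10.1 gives 17 and 25 patients, consistent with 40% of 42 = 16.8. The plan states no figure for the interaction, so there is none to reproduce.

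**Assumed inputs.** The documents give no marker means or SDs. I assume lognormal markers, a 50% fall in both groups from day -1 to day 28, and between-patient log-SD 0.5. Within-patient log-SD is 0.3, either at each visit (A) or at the second visit only (B).

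**Step 1, size of the raw interaction.** For a common proportional fall *f*, the raw interaction is *f* × (Group 1 baseline − Group 0 baseline). With Group 1 at 1000 units and *f* = 0.5:
- Group 0 at 800: 0.5 × 200 = 100 units
- Group 0 at 500: 0.5 × 500 = 250 units

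On the log scale the interaction is ln 0.5 − ln 0.5 = 0 in both cases.

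**Step 2, how often it is significant.** With two time points and complete data, the time-by-group test equals a two-sample t-test on the change. Two-sided 5% level, 20,000 simulated trials per setting:

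| Baseline ratio, Group 0 to Group 1 | Raw, A | Raw, B | Log, A or B |
|---|---|---|---|
| 1.0 | about 5% | about 5% | about 5% |
| 0.8 | 9% | 17% | about 5% |
| 0.7 | 18% | 37% | about 5% |
| 0.6 | 33% | 64% | about 5% |
| 0.5 | 54% | 88% | about 5% |

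A second set of assumptions (falls of 30–60%, between-/within-patient CV of 40%/20% or 60%/30%) gives raw rates of 6–21% at ratio 0.8 and 19–96% at ratio 0.5. The log rates are 4.7–5.3% throughout.

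**Step 3, power with equal baselines.** Suppose Group 0 retains a further 30% less: 0.5 × 0.7 = 0.35 of baseline, against 0.5 in Group 1. The log difference is ln 0.7 = −0.357. Under A, the SD of the log change is 0.3 × √2 = 0.424 and its standard error is 0.424 × √(1/17 + 1/25) = 0.133, a signal of about 2.7 standard errors. Simulated power is 74% log and 18% raw. Under B it is 96% and about 33%.

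**Step 4, ALC itself.** Here the groups are formed from the marker being tested. With the same proportional fall in everyone and the lowest 17 of 42 post-radiotherapy values placed in Group 0, the interaction is significant in 46% of trials on the log scale and 28% on the raw scale under A. With a fixed cut at 500 and the CV assumptions above, the rates are 37–40% log and 44–79% raw. Neither scale is valid for this comparison.

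**Step 5, a separate subset correlated with ALC.** With groups formed by post-radiotherapy ALC, the same proportional fall in everyone and patient-level correlations of 0.5/0.7/0.9, raw rejection is about 18/34/55% and log rejection about 5%. This assumes that the subset's visit-to-visit noise is independent of that in ALC.

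**The case against.** **The plan never says the data will be untransformed.** This stands. A mixed model on logged values, or a GEE with a log link, would fit the wording. A reader might infer that section 10.2 commits to raw values; the documents support only that no scale is fixed and that untransformed is the default reading.

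**A raw-scale interaction is not false if absolute falls do differ.** This also stands. It misleads only when the question is whether the proportional response differs.

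**Not every marker is exposed.** A reader might infer that all the secondary immune results would be artefacts. Nothing in the documents shows that cytokines, neutrophils or monocytes differ at baseline by ALC group, and with equal baselines the raw test keeps about 5% error. For such markers the issue is lost power.

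**The reach is limited.** DFS and OS use Cox regression and are untouched. The objectives in section 2.2.1 ask for marker change overall and by site, volume, dose, immunosuppression and toxicity; none asks for change by ALC status. That interaction appears only in section 10.2, which nevertheless makes it the effect of interest.

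**GEE.** Uncorrected sandwich tests reject in about 6.0–6.8% instead of 5% at this sample size. That does not justify removing the option.

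**Conclusion.** The concern holds as a gap in pre-specification: the plan targets an interaction without naming its scale. For lymphocyte-related markers, the default reading could turn an equal proportional fall into a significant interaction in about 9–54% of trials (noise at both visits) or 17–88% (noise at the second visit only) at baseline ratios from 0.8 to 0.5. A log-scale test stays at about 5% when group membership is independent of the marker's own noise. These sizes rest on assumed variances, falls and baseline gaps.

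A reader might also infer that taking logs repairs the whole analysis. It does not for ALC, which defines the groups, or for NLR, which has ALC as its denominator. Subsets that form a direct part of ALC need the same caution.

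The time-point conflict comes first: with sampling only at day -1 and day 28, the model described in section 10.2 cannot be fitted to these markers.

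**What to change.** In section 10.2:
- Reconcile the model's time points (day 28 and 24 months) with the sampling in sections 2.2.2, 4.1 and 6 and the schedule (day -1 and day 28).
- Pre-specify log-transformed analysis of absolute counts and cytokines, and of NLR wherever it is modelled (not against ALC status, see below). Report interactions as ratios of geometric means.
- Give a rule for zeros and values below the detection limit.
- State whether flow subsets are recorded as counts or percentages, and the scale for percentages and for the IFN signature.
- Do not test ALC or NLR against status defined by post-radiotherapy ALC, and flag the directly ALC-dependent subsets as needing cautious reading.
- If GEE is kept, name a small-sample correction (a minor point).

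The cost is wording only: no extra patients, samples or visits, provided the time points are aligned to the existing sampling. The downside is that effects are read as ratios rather than cell counts, and low values need an offset or a censoring rule.
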